11.6 Maintenance of the Study Blind and Unblinding

All study treatments will be double-blinded during the 52-week study; neither the subject nor the study site personnel will know which treatment is being taken. Each subject's treatment will be given a unique code number, traceable to the identity, dose, and batch number of the study medication. The IWRS will be used to hold treatment codes for each subject. The codes will only be accessible to authorized unblinded IWRS users.

The IWRS should not normally be accessed with a request to break the treatment code for reasons other than safety or in an emergency. Should the Investigator wish to break the code for such reasons, he/she are advised to consult the Sponsor (or designee) in advance where feasible. If this is not possible, the Investigator may access the IWRS to obtain the treatment code and provide the system with the reason for breaking the blind. The Sponsor should be notified as soon as possible thereafter. If the blind is broken for any individual subject, the subject must be withdrawn from the study, and any procedures accompanying withdrawal will be performed (Section 8.5).

The Sponsor and study team will remain blinded throughout the duration of the double-blind treatment of the study.

Because PK analysis will only be performed on samples from subjects receiving active medication, unblinded randomization codes will be given to PK lab.

An electronic list of randomization codes will be retrieved from IWRS and transferred to the Sponsor at the end of the study.

Since melanin density values could potentially be unblinding, adequate measures will be taken to protect the spectrophotometry data from disclosure to the sponsor and the study team until the end of the study. Melanin density component data will be measured by the dedicated unblinded site staff, securely uploaded to and processed by the dedicated unblinded data management team. The data handling procedure for melanin density will be described in the data management plan.

The handling of data that could potentially unblind the study will be defined in relevant study procedures documents (e.g., Unblinded Data Management plan or equivalent).

If study subjects elect to participate in the 26-weeks DBE after end of Visit 7 (EOT/Rand), subjects will remain blinded and subjects will be re-randomized. Subjects that received MT-7117 during the blinded period will continue the DBE in the same treatment arm and remain blinded. Subjects that received placebo will be randomized to receive MT-7117 [REDACTED] or [REDACTED] in 1:1 ratio for the 26 weeks DBE period. For subjects with [REDACTED], the [REDACTED] dose will be administered without re-randomization and will not be blinded during the extension period.

MT-7117 and placebo [REDACTED] will be physically identical in appearance and will be packaged identically and suitably labeled to maintain the blind for both the 26-week double-blind treatment period and the 26-week DBE treatment period.

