8.5 Withdrawal of Individual Subjects

A subject will be withdrawn from study if ANY of the following criteria are met:

1. The subject requests to voluntarily withdraw from further participation in study.
2. The subject is significantly noncompliant with the protocol.
3. Continuing in the study would be detrimental to the subject's safety in the opinion of the Investigator, e.g.,
 - a. The subject experiences intolerable AEs, SAEs, or AESIs.
 - b. The subject has clinically significant changes in safety parameters at any of the post-dose time points, as confirmed with a repeat assessment performed as soon as possible after the initial out-of-range result.
 - c. The subject experiences any clinically significant adverse findings from postbaseline nevi evaluation and adverse change is demonstrated histologically and confirmed by central pathologist. Visual evaluation of change will not be acceptable criteria for permanent discharge from treatment (Section 10.9.4).
 - d. Development of any clinically significant liver dysfunction, as follows:
 - i. ALT or AST $>8 \times$ ULN.
 - ii. ALT or AST $>5 \times$ ULN for more than 2 weeks.
 - iii. Elevated total bilirubin $>2 \times$ ULN and ALT or AST $>3 \times$ ULN or
 - iv. Symptoms consistent with liver dysfunction (e.g., fatigue, nausea, vomiting, abdominal pain or tenderness, fever, rash, eosinophilia $>5\%$) with concomitant ALT or AST values $>3 \times$ ULN.

Subjects meeting the laboratory criteria of ALT/AST and total bilirubin defined above (with or without alternative etiology), regardless of whether clinically significant or not, should be reported as a hepatic AE of special interest (AESI) (see Section 12.3). The Investigator should discuss with the Sponsor Medical Monitor about the determination of etiology and the potential of withdrawal. The abnormal laboratory values should be confirmed by repeated measurements at local or central laboratory as soon as possible (i.e., within 7 days after the first observation).

Any other laboratory or clinical abnormality that the Sponsor Medical Monitor and/or Investigator considered as clinically significant should be considered as potential reason for withdrawal.

These subjects will be discontinued from treatment but may be followed per protocol (see

Section 12.6). In addition, a subject may be withdrawn from treatment at any time for reason(s) other than those listed here. Subjects who have withdrawn from study drug cannot resume study drug.

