Subjects who are permanently withdrawn from study drug early should be encouraged to continue in the study and complete all other study assessments without receiving study drug. In case a subject withdraws from treatment and elects not to continue in the study, every attempt should be made to have the patient complete an early termination visit (Visit 7 or Visit 11) within 14 days of withdrawal, and follow-up visit assessments (Visit 12) at 6 weeks after early termination visit. However, PK blood samplings are not required for these subjects if their last dose of study medication is 7 days or more before the time point of PK blood samplings.

If a subject is discontinued prematurely from the treatment or the study, the date the subject is withdrawn from the treatment and the study and the reason for withdrawal from the treatment and the study will be recorded on the site source documents and in the electronic Case Report Form (eCRF).

In case of permanent discontinuation from study, the end-of-treatment and follow-up visit assessments should be performed, as completely as possible (Table 9-1). Unresolved AEs and SAEs will be followed up on according to Section 12.10. For discontinued subjects who will not revisit the clinic, the site will perform scheduled phone calls for the collection and source documentation for safety information (AEs, concomitant medication, and date of last dose of medication). Return of unused medication and any other materials (e.g., diary) will be performed by courier where allowed.

In the event that a subject elects not to return to the study site for the end of treatment or follow-up visit, the Investigator must make every effort to contact the subject to review/capture all AEs, assess dosing compliance, review concomitant medication, and make every effort to complete all end of study assessments.

Subjects withdrawn from the study following randomization onto double-blind treatment may not re-enter the study. Subjects withdrawn from treatment may remain on study and continue with study procedures off treatment based on the clinical discretion of the Investigator.

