14.1 Study Estimands

Primary Estimand

The primary estimand construction elements for this study are:

- Population: All randomized subjects who received at least 1 dose of study medication with baseline and post-randomization sunlight exposure diary assessment.
- Variable: Change from baseline in average daily sunlight exposure time (minutes) to first prodromal symptom associated with sunlight exposure between 1 hour post-sunrise and 1 hour pre-sunset at Week 26 (Visit 7).
- Inter-current event of treatment discontinuation using treatment policy: Regardless of early discontinuation of study drug due to any reason until the end of the double-blind treatment period.
- Population-level summary: Absolute mean difference in change from baseline in average daily sunlight exposure time (minutes) to first prodromal symptom between MT-7117 and placebo groups.

The primary estimand will be based on effectiveness assumption (de-facto) using treatment policy: The treatment effect will be attributable to the subject's initially randomized treatment regardless of treatment discontinuation.

Secondary Estimand

The secondary estimand construction elements to be tested as supportive analysis for this study are:

- Population: All randomized subjects who received at least 1 dose of study medication with baseline and post-randomization sunlight exposure diary assessment.
- Variable: Change from baseline in average daily sunlight exposure time (minutes) to first prodromal symptom associated with sunlight exposure between 1 hour post-sunrise and 1 hour pre-sunset at Week 26 (Visit 7).
- Inter-current event of treatment discontinuation using hypothetical strategy: If subjects could have treatment completion until the end of the double-blind treatment period.
- Population-level summary: Absolute mean difference in change from baseline in average daily sunlight exposure time (minutes) to first prodromal symptom between MT-7117 and placebo groups.

The secondary estimand will be based on efficacy assumption (de-jure) using a hypothetical strategy: The treatment effect will be attributable to the subject's initially randomized treatment if subjects could have stayed on study until the end of the double-blind treatment period.

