8.2.1 Primary Efficacy Endpoint

Primary Analysis

For the ITT1 population, the primary estimand will be tested including retrieved dropout data (after treatment discontinuation), using treatment comparisons of interest in change from baseline in average daily time to first prodromal symptom associated with exposure to sunlight between 1 hour post sunrise and 1 hour pre-sunset for the two MT-7117 doses (█ and █ █) compared with placebo at Week 26 (Visit 7).

To assess the treatment effect at Week 26, change from baseline in average daily time (minutes) to first prodromal symptom associated with exposure to sunlight between 1 hour post sunrise and 1 hour pre-sunset at Weeks 2, 4, 6, 8, 10, 12, 14, 16, 18, 20, 22, 24, and 26 will be analyzed using mixed-effect model for repeated measures (MMRM). The model will include fixed categorical terms for treatment, █

█ visit, and treatment by visit interaction together with continuous covariate terms for baseline average daily duration of sunlight exposure between 1 hour post sunrise and 1 hour pre-sunset to first prodromal symptom and baseline average daily duration of sunlight exposure between 1 hour post sunrise and 1 hour pre-sunset to first prodromal symptom by visit interaction. An unstructured (UN) correlation structure will be used to model the within-subject variance covariance errors. Should convergence of the model fail (due to the small numbers of

subjects in this study), the heterogeneous compound symmetry (CSH) and the heterogeneous Toeplitz structure (TOEPH), autoregressive [AR(1)] and compound symmetry (CS) correlation matrix will be used in that order instead of UN. The Kenward-Roger approximation will be used to estimate the denominator degrees of freedom. From the model described above, adjusted (least squares [LS]) means and standard errors will be produced by treatment group and visit. Difference in adjusted means at each visit (each MT-7117 dose vs. placebo) with standard errors, 95% CIs and associated p-values will also be produced. All available data from all subjects will be used in the primary analysis without any imputation.

Sensitivity Analysis

(1) Use of actual strata of baseline average daily sunlight exposure time to first prodromal symptom for randomization registration errors

In the above primary analysis model, [REDACTED]

[REDACTED] directly derived from e-Diary raw dataset.

(2) Controlled multiple imputation method

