The primary analysis model is using likelihood based approach to handle missing data under Missing At Random (MAR) missingness pattern in the primary estimand. In order to assess the robustness of the primary analysis also under Missing Not At Random (MNAR) pattern, a control group-based multiple imputation (MI) of the Pattern Mixture Model (PMM) method will be used. This model assumes MNAR for missing data mechanism in MT-7117 [REDACTED] and [REDACTED] and MAR for missing data mechanism in placebo on the ITT population.

- Step 1: This methodology will structure data based on missing data patterns. The PMM method will be based on a missingness pattern having a monotone structure, i.e. if among the observations over time one data value is missing, all other values after this missing value will also be missing. For patients with intermittent missing values, before performing MI based on the PMM, it will be necessary to create a monotone missingness pattern. Intermittent missing values will be imputed using the Markov Chain Monte Carlo (MCMC) methodology which assumes a multivariate normal distribution over all variables included in the imputation model. The MI procedure in SAS will be used for this purpose and this first MI step is planned to be repeated 100 times, creating different datasets with a monotone missing data structure. Seed value of 2022 will be used in the MI procedure. The imputation with the explanation variables of the baseline value and the post-baseline values is based on the MAR assumption, i.e. the missing data are assumed to follow the same model as the other patients. The minimum number

will be set as 0 because the imputed value for time to first prodromal symptom should be greater than or equal to 0.

The following SAS code will be used to generate the monotone missing data pattern:

[REDACTED]

- Step 2: After this, the remaining missing data will be imputed using a MI method for monotone missingness, with the assumption that the data on MT-7117 [REDACTED] and [REDACTED] once daily groups are MNAR and the data on placebo group are MAR. Control group-based assumption will be used for the missing data. Thus, for each of the created dataset with a monotone missing data pattern in step 1, the MI procedure in SAS will be used to impute missing values based on a sequential procedure reflecting the monotone missing data pattern. The MNAR statement of the following (see SAS code) will be used to generate the imputation.

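### Protocol 11.6 and the lead sentence of 8.5 take subjects out of the study, contradicting the retention wording in 8.5 and risking loss of the off-drug diary data that the treatment-policy primary estimand needs

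*Protocol*

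**What the plan says.** **Leaving the study.** Protocol 11.6 confines code breaks, normally, to safety reasons or an emergency, and then says: "If the blind is broken for any individual subject, the subject must be withdrawn from the study". It refers to the withdrawal procedures in 8.5. Protocol 8.5 opens: "A subject will be withdrawn from study if ANY of the following criteria are met". The criteria are the subject's own request, significant noncompliance, and safety grounds that include intolerable adverse events, nevus findings and liver criteria.

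**Leaving treatment only.** After that list, the same section says these subjects stop treatment but may be followed. It adds that subjects permanently off drug "should be encouraged to continue in the study and complete all other study assessments without receiving study drug", and that staying on study off treatment is at the investigator's clinical discretion. The Synopsis and 7.1 repeat the encouragement. Sections 10.9.4 (nevi) and 12.9 (pregnancy, citing 8.5) speak of ending treatment, not participation.

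**What the analysis needs.** Protocol 14.1 handles treatment discontinuation by treatment policy: "Regardless of early discontinuation of study drug due to any reason until the end of the double-blind treatment period". SAP 8.2.1 includes data collected after discontinuation in the primary MMRM and adds: "All available data from all subjects will be used in the primary analysis without any imputation". It describes the MMRM as resting on missing at random. A control-based multiple imputation is planned as a sensitivity analysis. The supportive analysis, for the hypothetical estimand, runs the same MMRM without the post-discontinuation data.

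**The concern.** A treatment-policy estimand is only as good as the off-drug follow-up behind it. A site that follows 11.6, or reads the first line of 8.5 literally, ends diary collection for subjects whose off-drug outcomes the estimand counts. A site that follows the later text of 8.5 keeps collecting. Missing data would then depend partly on which sentence a site acts on.

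For subjects lost this way, the MMRM predicts Week 26 from their earlier, mostly on-drug values and from others in the same arm. If benefit wanes after stopping, and stopping is more common on active drug, the estimate shifts in favour of the drug, toward what the supportive analysis targets. The two analyses would then agree partly because they use nearly the same data, and that agreement could be mistaken for robustness.

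**Working it through.** **1. The passages side by side**

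| Source | Consequence for the subject |
|---|---|
| Protocol 11.6, after a code break | Must leave the study; no exception |
| Protocol 8.5, lead sentence | Leaves the study on any criterion |
| Protocol 8.5, after the criteria | Stops treatment; may be followed |
| Protocol 8.5, Synopsis, 7.1 | Off drug: encouraged to continue |
| Protocol 8.5, final paragraph | May remain, at investigator discretion |
| Protocol 14.1, SAP 8.2.1 | Off-drug data counted to the end of the double-blind period |

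Section 11.6 conflicts with 14.1 outright. Section 8.5 conflicts with itself.

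**2. What a withdrawn subject may still contribute.** Section 8.5 asks for an early termination visit within 14 days and a follow-up visit 6 weeks later, and 10.7.1.1 has the diary kept until follow-up. At best that is 2 + 6 = 8 weeks of diary after withdrawal, which does not reach Week 26 for a subject who leaves early.

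**3. The plan's own figures** (Protocol 14.2: differences of 57 and 52 minutes, SD 79.3, 42 completers per group, 20% dropout)
- Effect sizes: 57/79.3 = 0.72 and 52/79.3 = 0.66, as stated.
- Power, first comparison: 90.9% (normal) or 90.2% (t), against 91% stated.
- Power, second comparison, requiring both rejections in fixed sequence: 79.0% by simulation, against 79% stated.
- Total: 42/0.8 = 52.5, rounded up to 53; 53 × 3 = 159, as stated.

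The sample size reproduces and does not depend on this point.

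**4. Size of the shift.** Let Δ be the on-drug difference, q the share of the active arm lost for these reasons, and f the fraction of effect kept off drug.
- Treatment-policy effect: (1 − q)Δ + q·f·Δ
- Effect if the lost subjects are credited in full: Δ
- Overstatement: q × (1 − f) × Δ

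The documents give neither q nor f, so both are assumed:

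| q | Δ = 57, f = 0 | Δ = 57, f = 0.5 | Δ = 52, f = 0 | Δ = 52, f = 0.5 |
|---|---|---|---|---|
| 1% | 0.57 min | 0.29 min | 0.52 min | 0.26 min |
| 5% | 2.85 min | 1.43 min | 2.60 min | 1.30 min |
| 10% | 5.70 min | 2.85 min | 5.20 min | 2.60 min |

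The formula gives the lost subjects full on-drug credit. If their own earlier values, or retrieved data from others, already show waning, the shift is smaller.

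**5. Power.** This is mainly a matter of bias. With about 61 randomized per group, 30% missing still leaves 61 × 0.7 = 42.7, that is 42 completers, the number planned.

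**The case against.** The best defence is that the protocol, read as a whole, intends retention. Only one sentence of 8.5 speaks of leaving the study. The rest of that section, the Synopsis, 7.1, 10.9.4 and 12.9 point to ending treatment with follow-up. The first criterion in 8.5, the subject's own request, is a proper study withdrawal. Code breaks are restricted and probably rare. The control-based imputation already asks what happens if active-arm subjects with missing data behave like placebo. Participation asks photosensitive patients to go outdoors, so the investigator may have safety reasons to end it.

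Most of this stands, and it limits the point. It does not remove the mandatory wording of 11.6 or the contradiction inside 8.5, and imputation cannot supply values that were never collected.

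Three stronger readings are tempting, and the documents do not support them:
- A reader might infer that collected data are discarded. Nothing orders that; values recorded before withdrawal stay in the MMRM. The loss is of data not collected afterwards.
- A reader might take 8.5 as a clear rule of removal. It is contradictory, and its later text favours retention.
- A reader might take the Phase 2 rate of discontinuation for adverse events in Protocol 5.2 (14.3% against 0% on placebo) and compute 0.143 × 57 = 8.2 or 0.143 × 52 = 7.4 minutes. That rate belongs to one redacted arm, and Protocol 7.4 says the two doses differed, so it cannot serve both. It counts subjects who stopped drug, not subjects lost from the study through this wording, and says nothing about code breaks. The product also assumes no follow-up and no retained effect.

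**Conclusion.** The point holds as an inconsistency that puts the primary estimand's data at risk. Section 11.6 requires study withdrawal after any code break, and the lead sentence of 8.5 contradicts the text that follows it. Both are at odds with a treatment-policy estimand analysed with retrieved off-drug data under missing at random.

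The effect on the estimate is q × (1 − f) of the true on-drug difference. At f = 0 that is 0.6 minutes at q = 1%, 2.9 at 5% and 5.7 at 10% of a 57-minute effect, and half as much at f = 0.5. This rests on assumed q and f, on lost subjects being credited with the full effect, and on losses that matter falling in the active arms. For code breaks alone, q is probably at the low end, though the documents give no count. The direction favours the drug if off-drug benefit wanes.

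**What to change.** Reconcile Protocol 8.5 and 11.6 with 14.1:
- Word both sections so that ending study drug, including after a code break, is distinguished from ending study participation.
- Make off-drug outcome collection to Week 26 consistent with the retention wording already in the Synopsis, 7.1 and 8.5.
- Leave unchanged the rules on when drug is stopped, the subject's right to leave, and the investigator's discretion on safety.

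This costs a wording change and adds no procedures.

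Protocol 8.1 reports that 184 subjects were randomized, and SAP section 7 describes the data review meetings as held, so new wording may come too late for many visits. For those, report by arm how many subjects left the study after a code break or on an 8.5 criterion other than their own request, and how many of them lack Week 26 diary data. Section 8.5 already requires separate dates and reasons for leaving treatment and leaving the study, so the counts can be made from existing records. They replace the assumed q with an observed one and show how much weight the control-based imputation has to carry.

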12 ADVERSE EVENT MANAGEMENT

All AEs and SAEs will be recorded in the source documents. All AEs and SAEs that occur from the time written informed consent/assent is obtained until the end of the follow-up period (6 weeks after the last treatment visit, for safety monitoring) will be recorded in the eCRF.

Even if the AE is assessed by the Investigator as not related to study medication, its occurrence must be recorded in the source documents and eCRF. AEs will be classified as occurring at 'baseline' if they occur before the administration of study medication. AEs will be classified as 'treatment-emergent' if they arise following the first administration of study medication in the double-blind treatment period (after randomization) or if a pre-dose AE increases in severity following dosing in the double-blind treatment period (after randomization).

At each study visit, after the subject has had an opportunity to spontaneously mention any problems, the Investigator or designee should inquire about the occurrence of AEs. The questioning should be open-ended and non-leading to avoid notifying either the subject or study site personnel of the actual treatment being administered.

